4.2.2.2 Restrictions on diet and life style

The usual restrictions on diet and life style that were already applicable for a given patient before entry into the trial, according to his/her medical condition, have to be continued.

4.2.2.3 Contraception requirements

Due to the advanced stage of disease of Phase I trial patient populations and the high medical need, females of childbearing potential can be included in this trial provided that they agree to use a highly-effective contraception method.

Females *not of childbearing potential* must have evidence of such by fulfilling one of the following criteria at screening:

- Documentation of irreversible surgical sterilization by hysterectomy, bilateral oophorectomy, or bilateral salpingectomy
- Post-menopausal: defined as more than 50 years-of-age and amenorrhoeic for at least 12 months following cessation of all exogenous hormonal treatments
- Women under 50 years-of-age would be considered postmenopausal if they have been amenorrhoeic for at least 12 months following the cessation of exogenous hormonal treatments, and have serum follicle-stimulating hormone and luteinizing hormone levels in the postmenopausal range for the institution.

WOCBP (trial participant or partner of a trial participant) must use a highly effective method of birth control per ICH M3 (R2) that results in a low failure rate of less than 1% per year when used consistently and correctly if their sexual partner is a man able to father a child.

These methods include:

- Total sexual abstinence when this is in line with the preferred and usual lifestyle of the study participant (periodic abstinence such as calendar, ovulation, symptothermal, post-ovulation methods and withdrawal are not acceptable methods of contraception), or
- Bilateral tubal ligation, or
- vasectomised partner (with appropriate post-vasectomy documentation of the absence of sperm in the ejaculate and provided that partner is the sole sexual partner of the female clinical trial participant), or
- Intrauterine device or intrauterine hormone-releasing system.

Women of childbearing potential must follow these methods during the trial and for at least 6 months after the end of the trial treatment.

Note: although hormonal contraception is considered a highly effective method of birth control, women of childbearing potential using a contraceptive pill must use an additional barrier method.

Men (trial participant or partner of a trial participant) must agree to use a condom, unless vasectomised with documented absence of sperm, and ensure that their female partner of childbearing potential is using an additional highly-effective method of birth control, during the trial and until at least 6 months after the end of the trial treatment.

Details of contraception methods may be adapted according to local requirements and are described in the patient information in the ICF.

4.3 TREATMENT COMPLIANCE

BI 1387446 and ezabenlimab (BI 754091) will be administered at the sites by the Investigator and/or trained site personnel, and dosing will be recorded in the eCRF. Therefore, actual dosing is expected to precisely follow the prescribed drug regimen. Missed or interrupted doses will be recorded in the eCRF with the associated reasons. The method of collecting dosing information assures that total exposure can be calculated programmatically taking into account any missing doses.

5. ASSESSMENTS

5.1 ASSESSMENT OF EFFICACY

The tumour response will be evaluated according to Response Criteria for Intratumoural Immunotherapy in Solid Tumours (itRECIST) ([R20-2734](#)). itRECIST criteria have been introduced recently and are tailored for solid tumours and intratumoural therapy trials. itRECIST criteria incorporate features of RECIST 1.1 ([R09-0262](#)) and iRECIST ([R17-0923](#)) with the intent to capture both systemic and local effects of intratumoural therapy. Thus, injected lesions remain evaluable for overall response assessment as long as these are integral to the intratumoural treatment regimen. As with RECIST 1.1, the classification algorithm follows the quantitative and qualitative assessment of tumour burden and defines the maximal number of target lesion (TL) tumours using the same measuring criteria as with RECIST 1.1. Importantly, the new criteria further categorize the target and nontarget tumour categories into injected and noninjected tumours (i.e., target injected (T-I), target noninjected (T-NI), nontarget injected (NT-I), and nontarget noninjected (NT-NI)). For details please refer to [Section 10.3](#) and the recently published paper by Goldmacher et al ([R20-2734](#)).

The assessment by the Investigator and/or the local radiologist will be the basis for continuation or discontinuation of the trial in an individual patient (in addition to safety). The baseline imaging must have been performed within 4 weeks prior to treatment with the trial medication and the Investigator will record the target and non-target lesions in the eCRF. Target lesions will be classified as target injected (T-I) or target non-injected (T-NI). The same method of assessment and the same technique must be used to characterise each

reported lesion at baseline and during treatment. Lesions in previously irradiated areas may not be considered measurable at baseline unless the lesions appeared after irradiation.

Tumour assessments will be performed as indicated in the [Flow Chart](#)

- at screening (as close as possible to the treatment start and no more than 28 days before the start of BI 1387446 in Arms A and B).
- before treatment administration at Cycle 2 Day 1 (a time window of -5 days is acceptable) in all treatment arms.
- before treatment administration (a time window of -7 days is acceptable) in C4, C6, C8, C10, C13, C16, C19, C23, C27, C31 and at EOT.

Copies of the scans will be collected by the sponsor or designee.

Additional imaging may be obtained at the discretion of the Investigator.

If the patient stops trial treatment prior to completion of maximum number administrations for a reason other than PD, the tumour assessment according to itRECIST will be performed according to standard of care until the last follow-up needed according to protocol.

All tumour imaging data acquired in this trial will be centrally collected by a CRO and centrally assessed by a designated core lab. Based on the centrally collected imaging data further integrated assessments of treatment-induced changes in imaging metrics, e.g. in tumour volume(s), shape(s), texture(s), will be performed. This so-called radiomics analysis is exploratory and will be performed by a service provider (CRO or academic) nominated by the Sponsor. Furthermore, centrally collected imaging data may be evaluated on an exploratory basis by a designated core lab to explore the impact of itRECIST on assessing efficacy outcomes over iRECIST/RECIST 1.1.

5.2 ASSESSMENT OF SAFETY

5.2.1 Physical examination

Physical examinations will be performed at screening, prior to trial medication administration on Day 1 of each cycle, at the EOT visit, and at the 30-day safety follow-up visit. However, patients will have an additional abbreviated physical examination (focused on the specific disease, at the Investigator's discretion) as indicated in the Flow Chart.

The physical examination will include measurement of height (screening only) and of body weight, and the evaluation of the ECOG performance score. Weight will be measured during screening and at each full physical examination (not during abbreviated physical examinations).

The ECOG score will be assessed at screening, on Day 1 of Cycles 1, 2 and 3, on Day 1 of every other cycle beginning with Cycle 5 prior to trial medication intake, at the EOT visit, and at the 30-day safety follow-up visit.

The results must be included in the source documents available at the site.

5.2.2 Vital signs

Vital signs will be evaluated at the time points specified in the [Flow Chart](#), prior to blood sampling.

This includes systolic and diastolic blood pressure and pulse rate (electronically or by palpation count for 1 minute) in a seated position after 5 minutes of rest. The results must be included in the source documents available at the site.

Vital signs will be monitored after drug administration as specified in [Section 4.1.4.5](#) and [Section 4.1.4.6](#).

5.2.3 Safety laboratory parameters

Safety laboratory parameters will be analysed at a local laboratory. Safety laboratory examinations will include tests as listed in [Table 5.2.3: 1](#), and should be obtained at the time points specified in the Flow Chart.

Table 5.2.3: 1

Safety laboratory tests

Category	Parameters	Screen.	CxD1 EOT	other
Haematology	white blood cell count (WBC), haemoglobin, platelet count (PLT)	x	x	x
	haematocrit, red blood cell count (RBC), white blood cell differentiation preferably expressed in absolute values (neutrophils, bands, lymphocytes, monocytes, eosinophils, basophils, other if applicable)	x	x	
Coagulation	International Normalized Ratio (INR), activated Partial Thromboplastin Time (aPTT), Prothrombin Time (PT)	x	x	x
Biochemistry	Glucose, sodium, potassium, creatinine, AST, ALT, alkaline phosphatase, lactate dehydrogenase (LDH), creatine kinase (CK), total bilirubin. If total bilirubin is elevated: direct bilirubin. If CK is elevated: CK-MB (cardiac), Troponin I and myoglobin.	x	x	x
	calcium, phosphate, magnesium, chloride, bicarbonate (HCO ₃), urea, total protein, albumin, C-reactive protein	x	x	
	Troponin I or Troponin T ¹	x	C4	
	N-terminal pro BNP (brain natriuretic peptide) ²	x	C2 C4 C7	
	Cholesterol, triglycerides, c-peptide	x	x ³	

Table 5.2.3: 1

Safety laboratory tests (cont.)

Category	Parameters	Screen.	CxD1 EOT	other
	Creatinine clearance if creatinine is >1.5xULN	x		
Hormones	TSH, free T4		x	
Immunoglobulins	Serum immunoglobulin levels (IgG, IgM, IgA, IgE).	x	x ⁴	
Urinalysis	Dipstick analysis of pH, protein, glucose, blood, leucocytes, nitrite. In case of pathological findings further evaluation should be performed and results documented	x	x	
Pregnancy test	β-HCG testing in serum in females of childbearing potential	x	x	

1. One test to be selected per investigational site and patient and to be reported throughout
2. If Nt proBNP not available, it may be replaced with a decline in preference by mid-regional pro-ANP, total BNP or ANP. One test to be selected per investigational site and patient and to be reported throughout.
3. If clinically indicated
4. Obtained at all timepoints where lymphocyte typing is done (refer to the assessment of immune cell subsets (via FACS) in [Section 5.4.2](#) and in the [Flow Chart](#))

Cardiac markers (Troponin I or Troponin T, NTproBNP or listed substitutes) have to be obtained at screening, in the respective treatment cycle indicated in [Table 5.2.3:1](#), and as clinically indicated in other cycles. In case the patient develops clinical symptoms of cardiac insufficiency, cardiac markers should be obtained as appropriate in addition to the mandatory timepoints. The same markers as listed for mandatory timepoints should be obtained.

Unequivocal clinical symptoms of cardiac insufficiency should always trigger an unscheduled echocardiography. In the absence of unequivocal clinical symptoms, the following cut-offs for cardiac markers should be considered as guidance to trigger further diagnostic workup including assessment of left ventricular ejection fraction ([Section 5.2.5](#)):

- Troponin T: increase to more than 3x baseline/ULN or absolute value > 100 ng/L (> 0.1 ng/mL, > 0.10 µg/L)
- NTproBNP: increase to more than 2 x baseline/ULN or absolute value >600 pg/mL (> 600 ng/L)

Patients do not have to be fasted for the blood sampling for the safety laboratory.

Screening laboratory assessments performed within 72 hours of the first trial treatment administration are not required to be repeated on Cycle 1 Day 1. Other safety laboratory should be performed within 24 hours of the visits.

Instructions regarding sample collection, sample handling/ processing and sample shipping are provided in the Laboratory Manual in the ISF.

Clinically relevant abnormal findings as judged by the Investigator will be reported as adverse events (refer to [Section 5.2.7](#)).

In case the criteria for hepatic injury are fulfilled, a number of additional measures will be performed (refer to [Section 5.2.7.1.4](#) and the DILI Checklist provided in the eDC system). The amount of blood taken from the patient concerned will be increased due to this additional sampling.

5.2.4 [Electrocardiogram](#)

Standard 12-lead (I, II, III, aVR, aVL, aVF, V1 - V6) resting electrocardiograms (ECGs) will be digitally recorded at various time points throughout the trial. The [Flow Chart](#) outlines which visits will require ECGs, and Blood sampling Flow Chart outlines which time points require triplicate ECGs to be done along with certain PK samples (Arm A and B).

All ECGs will be obtained after the patient has been resting supine for at least 5 minutes prior to the indicated times. All ECGs should be recorded with the patient in the same physical position.

Electrocardiogram machines will be provided for the trial to facilitate central readings. Before study start, the study sites will be trained for the proper use of the equipment and transfer of the electronic data to the vendor. All ECGs will be transmitted to the central vendor for analysis.

ECGs may be repeated for quality reasons and the repeated recording will be used for analysis. If necessary, additional ECGs may be recorded for safety reasons.

The ECG recordings must also be analysed and checked for abnormality by the Investigator (or designated physician) who will also calculate the QTcF value for each time point as the mean of the 3 ECGs. Particular attention must be paid to T wave inversions. It is not mandatory to wait for central evaluation of ECGs to make clinical decisions. Clinically relevant abnormal findings will be reported either as baseline condition (if identified at the screening visit) or otherwise as adverse events and will be followed up and/or treated as medically appropriate. CTCAE Version 5 will be used for the grading of prolonged QTcF intervals.

In case of related ECG changes and whenever the Investigator deems necessary, additional ECG monitoring will be performed in the respective and later courses of treatment. The ECGs will be recorded using dedicated equipment provided by a vendor. The ECGs will be sent for evaluation by a central vendor. Data from this central review will be taken for retrospective data analysis. To allow for a heart rate correction of QT intervals the QT

intervals will be matched to the preceding RR intervals using at least QTcF (Fridericia's formula $QTcF = QT/RR^{-1/3}$) and QTcB (Bazett's formula $QTcB = QT/RR^{-1/2}$).

In case of QTcF prolongation to >500 ms (mean of 3 ECGs) AFTER receiving therapy, the Investigator will initiate further ECG monitoring and diagnostics (e.g. check electrolytes and check concomitant therapy that may be contributing to QTcF prolongation) and if required provide adequate treatment according to medical standards. The patient will be discharged from the investigational site only after resolution of ECG findings as assessed by the Investigator.

In case of occurrence of symptoms suggestive of arrhythmia related to QTcF prolongation, a cardiologic evaluation will be performed, and treatment will be provided according to medical standards at the discretion of the Investigator.

At timepoints when ECG and blood sampling for PK are planned at the same time, ECG should be performed prior to PK sampling. Triplicate ECGs should be performed within a maximum period of 5 minutes prior to blood sampling.

The centralised ECG evaluation will include the semi-automatic determination of the RR, PR interval, QRS complexes, and QT intervals.

All interval measurements in one patient will be performed on the same lead. The intervals will be measured from four cardiac cycles (beats) in lead II. If lead II shows a flat T wave or is not measurable for any reason, lead V5 will be used, or if that lead is not measurable, then lead I will be used for assessment of all ECGs.

Central morphological analyses of the ECGs (cardiologic assessments) will be performed by a board-certified cardiologist or equivalent. In case additional (unscheduled) ECGs due to safety reasons are recorded at the study site, all ECGs of this time point including the additional ECGs will undergo interpretation. The ECG interpretation will include an overall assessment (normal, abnormal, not assessable) as well as assessments concerning rhythm, conduction, presence of myocardial infarction, ST segment deviations, T wave morphology, and U wave morphology findings.

Abnormalities detected during centralised ECG evaluation will not necessarily qualify as AEs. In case of clinically relevant abnormalities (e.g. heart blocks or large changes in interval duration) the ECG core laboratory may contact the Investigator and vice versa. Centrally assessed ECGs will comply with the ICH E14 guidance document and supplements [[R05-2311](#), [R13-0801](#), [R13-4095](#)] as well as the FDA requirements for annotated digital ECGs [[R09-4830](#)].

5.2.5 Echocardiography / MUGA scan

Echocardiography to assess left ventricular (LV) function needs to be performed at screening and in regular intervals as indicated in the [Flow Chart](#). In case trial drugs are administered at the respective visit, echocardiography should be obtained prior to trial drug administration.

LV ejection fraction (LVEF) has to be measured and reported in the eCRF, additional relevant abnormal findings may be reported as baseline conditions/adverse events. Although echocardiography is the preferred method, MUGA scans are permitted to quantify LVEF. The same method should be used in a single patient throughout the trial.

In case the patient develops clinical symptoms of cardiac insufficiency, unscheduled echocardiography should be obtained as soon as possible to quantify LV ejection fraction and additional parameters as clinically indicated.

A clinically relevant decline in LVEF, defined as an absolute decrease by at least 10 percentage points, should be confirmed by a subsequent assessment after 1-2 weeks. A confirmed LVEF decline should be reported as adverse event. Upon detection of a clinically relevant decline in LVEF, BI 1387446 should be paused until LVEF returns to baseline, and should only be resumed at a reduced dose. In case of a recurrent decline upon re-exposure at a reduced dose of BI 1387446, treatment should be permanently discontinued. In case a clinically relevant decline in LVEF is observed, patients should be closely followed for signs of cardiac disease throughout the trial. Results from additional imaging studies should be captured in the eCRF.

5.2.6 Other safety parameters

Assessment of lens opacity

Ocular history as part of the medical history will be reviewed at screening. Examination of patients for the presence and extent of lens opacities using slit-lamp examination will be performed by an ophthalmologist at screening, at the 30-day safety follow and at any time during the treatment period, if clinically indicated. Lens opacities as seen on clinical slit-lamp examination will be graded and documented according to the Lens Opacities Classification System III (LOCS III) ([R99-2093](#)).

5.2.7 Assessment of adverse events

5.2.7.1 Definitions of AEs

5.2.7.1.1 Adverse event

An AE is defined as any untoward medical occurrence in a patient or clinical investigation subject administered a medicinal product and which does not necessarily have to have a causal relationship with this treatment.

An AE can therefore be any unfavourable and unintended sign (including an abnormal laboratory finding), symptom, or disease temporally associated with the use of a medicinal product, whether or not considered related to the medicinal product.

The following should also be recorded as an AE in the CRF and BI SAE form (if applicable):

- Worsening pre-existing conditions, excluding disease progression.

- Changes in vital signs, ECG, physical examination and laboratory test results, if they are judged clinically relevant by the Investigator.

If such abnormalities already exist prior to trial inclusion, they will be considered as baseline conditions and should be collected in the eCRF only.

5.2.7.1.2 Serious adverse event

A serious adverse event (SAE) is defined as any AE, which fulfils at least one of the following criteria:

- results in death,
- is life-threatening, which refers to an event in which the patient was at risk of death at the time of the event; it does not refer to an event that hypothetically might have caused death if more severe,
- requires inpatient hospitalisation or prolongation of existing hospitalisation
- results in persistent or significant disability or incapacity,
- is a congenital anomaly / birth defect,
- is deemed serious for any other reason if it is an important medical event when based on appropriate medical judgement which may jeopardise the patient and may require medical or surgical intervention to prevent one of the other outcomes listed in the above definitions. Examples of such events are intensive treatment in an emergency room or at home for allergic bronchospasm, blood dyscrasias or convulsions that do not result in hospitalisation or development of dependency or abuse.

5.2.7.1.3 AEs considered “Always Serious”

In accordance with the European Medicines Agency initiative on Important Medical Events, Boehringer Ingelheim has set up a list of further AEs, which by their nature, can always be considered to be “serious” even though they may not have met the criteria of an SAE as defined above.

The latest list of “Always Serious AEs” can be found in the eDC system. A copy of the latest list of “Always Serious AEs” will be provided upon request. These events should always be reported as SAEs as described above.

5.2.7.1.4 Adverse events of special interest

The term adverse events of special interest (AESI) relates to any specific AE that has been identified at the project level as being of particular concern for prospective safety monitoring and safety assessment within this trial, e.g. the potential for AEs based on knowledge from other compounds in the same class. AESIs need to be reported to the sponsor’s Pharmacovigilance Department within the same timeframe that applies to SAEs, please see [Section 5.2.7.2.2](#).

The following are considered as AESIs:

Dose limiting Toxicities (DLTs)

All DLTs are considered to be AESIs, and must be reported as such. The definition of DLT is presented in [Section 4.1.4.4](#).

Hepatic injury and drug-induced liver injury (DILI)

During the course of the trial the Investigator will remain vigilant for increases in liver biochemistry. The Investigator is responsible for determining whether a patient meets the hepatic injury definition or potential Hy's law criteria at any point during the trial.

The Investigator participates, together with the Medical Monitor and clinical project representatives, in review and assessment of cases meeting potential hepatic injury and Hy's law criteria. Hy's law criteria are met if there is no alternative explanation for the elevations in liver biochemistry other than a DILI caused by the investigational product.

The Investigator is responsible for recoding data pertaining to these cases and for reporting them as AEs and/or SAE according to the outcome of the review and assessment in line with standard safety reporting processes.

Hepatic injury definition:

A hepatic injury is defined by the following alterations of hepatic laboratory parameters in patients with normal liver parameters at baseline (ALT, AST, and bilirubin within normal limits):

- an elevation of AST and/or ALT ≥ 3 fold ULN combined with an elevation of total bilirubin ≥ 2 fold ULN measured in the same blood draw sample, or in samples drawn within 30 days of each other, or
- aminotransferase (ALT, and/or AST) elevations ≥ 10 fold ULN

For patients with abnormal aminotransaminase levels between >1 and <3 x ULN at baseline:

- An elevation of AST and / or ALT ≥ 3 -fold the baseline value combined with an elevation of bilirubin ≥ 2 -fold ULN or ≥ 2 -fold the baseline value (if bilirubin is elevated at baseline), measured in the same blood sample, or in samples drawn within 30 days of each other; or;
- Aminotransferase elevations ≥ 5 -fold the baseline value.

For patients with abnormal aminotransaminase levels between ≥ 3 x ULN and <5 x ULN at baseline:

- An elevation of AST and / or ALT ≥ 2 -fold the baseline value combined with an elevation of bilirubin ≥ 2 -fold ULN or ≥ 2 -fold the baseline value (if bilirubin is elevated at baseline); measured in the same blood sample or in samples drawn within 30 days if each other; or;
- Aminotransferase elevations ≥ 3 -fold the baseline value.

Hy's Law cases have the following 3 components:

- The drug causes hepatocellular injury, generally shown by a higher incidence of 3-fold or greater elevations above the ULN of ALT or AST
- Among trial subjects showing such aminotransferase elevations, often with elevations much greater than 3 times ULN, one or more also show elevation of serum total bilirubin to >2 times ULN, without initial findings of cholestasis (elevated serum ALP)
- No other reason can be found to explain the combination of increased aminotransferase and total bilirubin, such as viral hepatitis A, B, or C; pre-existing or acute liver disease; or another drug capable of causing the observed injury.

These lab findings constitute a hepatic injury alert and the patients showing these lab abnormalities need to be followed up according to the "DILI checklist" provided in the eDC system.

In case of clinical symptoms of hepatic injury (icterus, unexplained encephalopathy, unexplained coagulopathy, right upper quadrant abdominal pain, etc.) without lab results (ALT, AST, total bilirubin) available, the Investigator should make sure these parameters are analysed, if necessary in an unscheduled blood test. Should the results meet the criteria of hepatic injury alert, the procedures described in the DILI checklist should be followed.

Lab values meeting the hepatic injury definition will need to be reported as AESI. Please follow the flowchart below for reporting hepatic injury / potential DILI cases

[figure not shown]

Figure 5.2.7.1.4: 1 Processing Potential DILI Cases in Oncology

Immune related adverse events (irAE)

Immune-related AEs are AEs associated with immunotherapy treatments that appear to be associated with the immune therapy's mechanism of action. These adverse reactions, which can be severe, may involve the gastrointestinal, skin, liver, endocrine, respiratory, renal, or other organ systems. All immune-related events are to be reported as AEs. Some irAEs also need to be reported as AESIs as defined by the sponsor in [Table 10.1.1: 1](#). If an Investigator determines a grade 3 event (not on the list) to be immune-related, the Investigator should also report that event as an AESI.

Recommendations for the management of irAEs are presented in [Appendix 10.2](#).

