 - a. absolute neutrophil count (ANC) $\geq 1.5 \times 10^9/L$ ($\geq 1.5 \times 10^3/\mu L$, $\geq 1,500/mm^3$)
 - b. platelet count $\geq 100 \times 10^9/L$ ($\geq 100 \times 10^3/\mu L$, $\geq 100 \times 10^3/mm^3$)
 - c. haemoglobin $\geq 90 \text{ g/L}$ ($\geq 9.0 \text{ g/dL}$, $\geq 5.6 \text{ mmol/L}$)
 - d. total bilirubin ≤ 1.5 times the upper limit of normal (ULN), except for patients with Gilbert's syndrome: total bilirubin $\leq 3 \times \text{ULN}$ or direct bilirubin $\leq 1.5 \times \text{ULN}$.
 - e. alanine aminotransferase (ALT)/Aspartate aminotransferase (AST):
 - patients without liver metastases: ALT/AST $\leq 2.5 \times \text{ULN}$
 - patients with liver metastases with planned injection into liver lesion: ALT/AST $\leq 2.5 \times \text{ULN}$
 - patients with liver metastases without planned injection into liver lesions: ALT/AST $\leq 5 \times \text{ULN}$
 - f. Creatinine $\leq 1.5 \times \text{ULN}$. If creatinine is $> 1.5 \times \text{ULN}$, patient is eligible if concurrent creatinine clearance $\geq 45 \text{ ml/min}$ ($\geq 0.045 \text{ L/min}$) (measured or calculated by CKD-EPI formula). ¹
 - g. prothrombin time (PT) $\leq 1.5 \times \text{ULN}$
 - h. activated partial thromboplastin time (aPTT) $\leq 1.5 \times \text{ULN}$

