#### Hepatic enzyme elevations (potential Hy's law cases):

These are defined as those cases where a combination of all of the following events occurred: any on-treatment value of ALT and/or AST > 3ULN (upper limit of normal) with total bilirubin  $\geq$  2ULN and ALKP < 2ULN. The events can occur in any order, but must occur within 30 days of the previous event, i.e. the second event must occur within 30 days of the first event, and the third event must occur within 30 days of the second event, etc. Patients with missing laboratory values for liver enzymes will be excluded from these analyses, but presented separately.

Proprietary confidential information © 2024 Boehringer Ingelheim International GmbH or one or more of its affiliated companies.

A listing of patients with hepatic injuries according to CTP Section 5.2.7.1.4 will be provided.

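### The hepatic injury definition has no baseline group for eligible patients with normal ALT/AST and raised bilirubin, so an isolated aminotransferase rise in them meets no criterion and is absent from the SAP listing

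*Protocol*

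**What the plan says.** Protocol Section 5.2.7.1.4 gives different hepatic injury thresholds according to liver values at baseline.

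- **Group 1** applies "in patients with normal liver parameters at baseline (ALT, AST, and bilirubin within normal limits". Its limbs are ALT/AST at least 3 x ULN with bilirubin at least 2 x ULN, or ALT/AST at least 10 x ULN alone.
- **Group 2** begins "For patients with abnormal aminotransaminase levels between >1 and <3 x ULN at baseline". Its limbs are ALT/AST at least 3 times baseline with a bilirubin rise, or at least 5 times baseline alone.
- **Group 3** covers baseline aminotransferases from 3 to below 5 x ULN. Its limbs are at least 2 times baseline with a bilirubin rise, or at least 3 times baseline alone.

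Only groups 2 and 3 have a baseline-relative bilirubin alternative, available "if bilirubin is elevated at baseline".

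Eligibility is wider. Criterion 11d in Section 3.3.2 allows total bilirubin up to 1.5 x ULN, "except for patients with Gilbert's syndrome", who may enter at up to 3 x ULN total or with direct bilirubin up to 1.5 x ULN. Criterion 11e allows ALT/AST up to and including 5 x ULN in patients with liver metastases and no planned liver injection.

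Section 5.2.7.1.4 ties the hepatic injury alert, DILI checklist follow-up and AESI reporting to these findings. Section 5.2.7.2.4 adds that qualifying laboratory values are AESIs even when progression is the likely explanation. SAP Section 7.8.2 takes the definition over by reference: "A listing of patients with hepatic injuries according to CTP Section 5.2.7.1.4 will be provided".

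**The concern.** The three groups do not cover everyone whom criterion 11 admits. Normal ALT/AST with bilirubin above ULN fails group 1 on bilirubin and fails groups 2 and 3 on aminotransferases. The limb for an isolated aminotransferase rise therefore does not exist for these patients, and a combined rise counts only if it satisfies the separate Hy's law text.

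This looks like a drafting slip. Groups 2 and 3 provide for raised baseline bilirubin. The hepatitis guidance in Section 10.1.2 has a tier for eligible patients entering with raised bilirubin. The log for Global Amendment 2 says the definition was revised to serve patients with abnormal liver parameters at baseline.

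At stake are the hepatic injury classification, the checklist trigger, the AESI rule that applies whether or not progression is blamed, and the completeness of one SAP safety listing in a first-in-human trial.

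**Working it through.** No sample size or error rate is involved, and the plan states no figure to reproduce. The check applies the definition to baseline values that criterion 11 allows. Inputs are the thresholds in Section 5.2.7.1.4, criteria 11d and 11e, and the Hy's law rule in SAP 7.8.2. All values are multiples of ULN.

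**Step 1: group, and threshold for an isolated rise.** The last column takes on-treatment ALT of 12 with bilirubin unchanged from baseline.

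| Baseline ALT/AST | Baseline bilirubin | Group | Isolated-rise threshold | ALT 12 qualifies? |
|---|---|---|---|---|
| 1.0 | 1.0 | 1 | 10 | yes |
| 1.0 | 1.2 | none | none | no |
| 1.0 | 1.5 | none | none | no |
| 1.1 | 1.2 | 2 | 5 × 1.1 = 5.5 | yes |
| 2.5 | 1.2 | 2 | 5 × 2.5 = 12.5 | no, but a threshold exists |
| 4.9 | 1.2 | 3 | 3 × 4.9 = 14.7 | no, but a threshold exists |
| 5.0 | 1.0 | none | none | no |

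Rows 2 and 4 show the anomaly. At the same bilirubin, a patient entering with ALT 1.1 is flagged from 5.5, while one entering with ALT 1.0 is not flagged at any isolated ALT.

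**Step 2: does the Hy's law wording close the gap?** Take baseline ALT/AST normal, bilirubin 1.2, on-treatment ALT 12.

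- Bilirubin stays below 2: the protocol's Hy's law text needs more than 2, and the SAP rule needs at least 2. Neither applies.
- Bilirubin above 2, no initial cholestasis, no other cause: the protocol text applies and has no baseline condition. The SAP rule also applies if ALKP is below 2.
- Bilirubin above 2 with cholestasis: the protocol text excludes it, and the SAP rule excludes it if ALKP is at least 2. Group 1's combined limb has no cholestasis condition, so the same rise would qualify in a patient with normal baseline bilirubin.

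The gap is therefore the isolated rise, plus combined rises outside the Hy's law text.

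**Step 3: effect of regrouping.** With group 1 defined by normal ALT and AST only, ALT 12 meets its existing limb (12 ≥ 10) at every baseline bilirubin from 0.8 to 3.0. With group 3 extended to include 5.0, that patient gains an isolated-rise threshold of 3 × 5 = 15 and a combined-limb threshold of 2 × 5 = 10.

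**Step 4: the bilirubin limb in Gilbert's syndrome.** A patient eligible at bilirubin 2.5 already meets a limb of at least 2 at entry, so ALT of 3 alone would count as a combined injury. A limb of twice baseline would be 2 × 2.5 = 5.0. For baseline 1.2 it would be 2 × 1.2 = 2.4.

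**The case against.** The best reply is that such an event would rarely go unseen.

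- All DLTs are AESIs, and the criteria in Section 4.1.4.4 have no baseline-bilirubin condition. They include Grade 4 or higher ALT/AST and a combined ALT/bilirubin criterion, and the general Grade 3 criterion may also apply.
- Table 10.1.1:1 makes immune-related transaminase elevations of Grade 2 or higher AESIs.
- The hepatitis guidance in Section 10.1.2 asks for a work-up of other causes and points to the DILI section.
- The SAP's Hy's law analysis, CTCAE shift tables and tables of clinically significant abnormalities have no baseline group.
- The checklist and the processing flowchart cannot be inspected here.

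Most of this stands and limits the consequence, but it does not close the gap. The immune-related route depends on attribution, and the DLT definition excludes events unequivocally due to the malignancy. The rule in Section 5.2.7.2.4 exists to remove that dependence, yet it refers back to the incomplete definition. Reporting by another route does not make the event a hepatic injury for the alert or the listing.

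A reader might infer that everyone entering with raised bilirubin is without an alert. The documents do not support that: raised bilirubin with ALT/AST above 1 and below 5 x ULN is covered. Nor do they support saying that ALT of 12 x ULN can never be an alert in the ungrouped patients, because the Hy's law text can still apply.

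A head count is also tempting. An assumed 5% to 15% with this baseline pattern gives 78 × 0.05 = 3.9 to 78 × 0.15 = 11.7 patients. That prevalence is in neither document, and the result counts patients with the trait, not missed events. With a further assumed 1% to 5% having a qualifying rise, the expected number is about 0.04 (3.9 × 0.01) to 0.6 (11.7 × 0.05).

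**Conclusion.** The gap is real on the text. Two kinds of eligible patient fit no baseline group: those with normal ALT/AST and bilirubin above ULN, and those at exactly 5 x ULN. The second is a single boundary value.

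For the first kind, an isolated aminotransferase rise, or a combined rise outside the Hy's law text, is not hepatic injury as defined. On that basis it triggers neither the DILI checklist nor the AESI rule that applies despite suspected progression, and it is not in the SAP 7.8.2 listing.

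The size can be given only as a contrast: ALT of 12 x ULN qualifies at baseline bilirubin 1.0 x ULN and does not at 1.2 x ULN. The number of patients is not given. The conclusion rests on reading the group conditions literally and on the flowchart and checklist not adding a wider trigger. No primary or secondary endpoint is affected.

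**What to change.** Reconcile Section 5.2.7.1.4 with inclusion criterion 11 so that every eligible patient falls in exactly one group:

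- Define group 1 by ALT and AST within normal limits, keeping its existing limb of at least 10 x ULN.
- Make the upper bound of group 3 at most 5 x ULN, to match 11e.
- State that when baseline bilirubin is raised, the baseline-relative bilirubin limb applies in place of the ULN limb. Copying the either/or wording of groups 2 and 3 into group 1 would let Gilbert's patients at or above 2 x ULN meet the limb on entry.

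SAP Section 4 records that development has been terminated. If the protocol is not amended again, add a sentence to SAP 7.8.2 applying the same grouping to the hepatic injury listing. That repairs the listing but not the alert or the checklist trigger.

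The cost is wording in one section and no new test. A few more alerts and DILI checklists may follow. The in-place-of rule also raises the bilirubin limb for modest elevations (2.4 rather than 2 x ULN at baseline 1.2 x ULN), although the Hy's law text would still cover non-cholestatic rises above 2 x ULN.
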